## **5.4 Tissue Banking**

Blood samples will be drawn from participants and analyzed for biomarkers of depression and response to treatment. Samples will be stored in a -80 freezer in [name] laboratory at [name] or in [name] laboratory in the Department of Anesthesiology, U of U School of Medicine.

Participants who consent to bank de-identified samples will be assigned a study code that is linked to their identifying information during the study period. After all study blood analyses are performed, the study coordinator will determine which samples (by code) need to be de-identified. When these samples are located, they will be assigned a new code that is not linked to personal identifiers. This de-identification process will happen after all study blood analyses are completed.

Participants who want their samples to be removed from the bank must contact [name]. If their samples are still linked to identifying information, they will be located and destroyed. De-identified samples will not be removed, as it will not be possible to identify their source.

De-identified banked samples will be available to researchers within the University of Utah and at the institutions of research collaborators. All researchers must contact [name] to receive permission to conduct IRB approved research on depression and response to treatment using these samples.

## **6. Data and Safety Monitoring**

We will monitor study data and documentation after the first 2 participants have completed treatment and then every 6 months thereafter. The monitoring group will consist of [name], MS, Professor of Anesthesiology; [name], Associate Professor (Clinical) of Anesthesiology; and [name], Associate Professor (Clinical) of Psychiatry. This group is well qualified to review data and safety reports for the study.

### **6.1 Data Collection**

Discussion of the study with participants will take place individually instead of in front of a group. The data collected through research interventions will be conducted in a private place. The information collected about participants will be limited to the amount necessary to achieve the aims of the research so that no unneeded information will be collected. Gene expression data gathered during this study will not be shared with the participant or family members.

### **6.2 Data Storage**

Research data will be stored on password protected computers or in locked cabinets or offices. All participant identifiers will be stored separately from the coded, participant data.

Any data that will be transferred or transported outside of the institution will be encrypted. Any research information shared with outside universities or entities will be de-identified.

Periodic review and confirmation of participant eligibility and informed consent documentation will take place. This review will also include confirmation that all appropriate information has been reported to the oversight agencies (IRB).

### **6.3 Safety and Efficacy Monitoring**

All serious adverse events will be reported within 5 days to the Data and Safety Monitoring Board (DSMB) and IRB by the Principal Investigator or study coordinators. These would include life-threatening cardiac arrhythmias, respiratory arrest, myocardial infarction, stroke, and death. Moderate adverse events including worsening of depressive symptoms will be reported to the DSMB. An interim data analysis will be performed at the midpoint of this pilot investigation, after data is obtained from 5 participants in each of the treatment conditions. The study will be terminated if significantly greater negative outcomes are associated with either isoflurane treatment or propofol treatment.

Prior to each treatment, participants will fill out the QIDS-SR. HRSD-24 will be obtained at baseline, before treatment 6, and after treatment 10. All participants will be assessed before the 6th treatment. If participants in Low ISO/BS- or propofol treatment groups show clinical deterioration (defined by 2 consecutive QIDS scores below baseline OR a decrease in HRSD-24 before the 6th treatment), they will be offered treatment at the 80% burst suppression level (High ISO/BS+) as it has proven effective in reducing depression or ECT as the standard of care treatment. Participants in High ISO/BS+ treatment who show clinical deterioration, as defined above, will be offered ECT. All serious adverse events will be reported within 5 days to the DSMB by the Principal Investigator or study coordinators. The DSMB will also be notified within 10 business days if a study participant is showing signs of clinical deterioration (defined as 2 consecutive QIDS scores below baseline OR HRSD-24 below baseline). Progress reports will be submitted every 6 months. If a participant has a serious reaction to anesthesia, they will be withdrawn from the study.

As exploratory biomarkers, we will evaluate whether quantitative cortical EEG changes early in treatment (obtained from dual lead BIS data in each treatment session) are associated with subsequent remission in depressive symptoms.

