## 2. Study Objectives

### 2.1 Study 1

Study 1 will test the central hypothesis that high dose isoflurane anesthesia inducing EEG burst suppression (High ISO/BS+) is a more effective intervention for severe depression when compared to a low dose isoflurane anesthesia that does not induce EEG burst suppression (Low ISO/BS-). The proposed study is a randomized, double-blind trial that will evaluate 30 actively depressed participants with moderate to severe depression. Depression outcomes will be compared between two groups of participants (n=15 per group) who have received 10 treatment applications over a period of three weeks of either High ISO/BS+ or Low ISO/BS-.

Aim 1. To determine whether High ISO/BS+ is more effective than Low ISO/BS- in producing either a treatment response (defined as 50% reduction in depression scores) or full remission of depressive symptoms. We hypothesize that significantly more depressed participants randomized to receive 10 treatments of High ISO/BS+ compared to Low ISO/BS- will show a positive treatment response or full remission by treatment end. Based on the STAR\*D Trial, a responder is a participant showing 50% reduction in depression score and full remission is defined as a score of 0-10 on the HRSD-24 scale and score of 0-5 on the QIDS-SR16.

Aim 2. Preliminary data on neural and immune pathways that are differentially affected by the 2 treatments and associated with antidepressant effects will be explored by comparing changes from pre-treatment to post-treatment in full transcriptome leukocyte gene expression (using the RNA Seq method).

Aim 3. To measure the central neurochemical effects of isoflurane treatment, we will quantify neurotransmitter levels (GABA and glutamate) using magnetic resonance spectroscopy.

### 2.2 Pilot Study 2

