### **4.3 Study Recruitment Procedures**

Potential participants will be recruited to the study through one of three ways: chart review, referral, or direct enrollment.

Recruitment via chart review: Potential participants will first be identified through review of medical records by trained study staff; specifically, examination of the records of patients who have been scheduled for an ECT consultation at the University Neuropsychological Institute (UNI). Participants who may be eligible for screening will be told about the study toward the end of their consultation. Interested patients will be screened and consented either right after the ECT consultation or during a separate appointment.

Recruitment via referral: Physicians from the Department of Psychiatry who have been informed of this study may also refer patients for screening. Patients who are referred will be contacted by study staff to arrange for screening and consent.

Direct enrollment: Psychiatrists listed on the study protocol may identify potential research volunteers during their ECT consultations. These patients will be informed of the research, and if interested, will be screened and consented.

Participants will be informed that there are two study options and that they will be able to decide which one they will participate in. For the isoflurane study, we will explain that some preliminary evidence shows that high dose isoflurane is effective in reducing depression symptoms. However, if the isoflurane study is chosen, there is a 50:50 chance of being in the low dose isoflurane treatment, and the individual will not know what treatment group (high vs low dose) they are in. We do not know whether low dose isoflurane will reduce depression symptoms. For the propofol study, we will explain that this arm of the study is open-label, meaning they will know they are receiving propofol treatment at a dose that produces burst suppression. We will also inform participants that we do not know if propofol treatment will be effective in reducing symptoms of depression.

We hope to enroll at least 1 participant per week and have a maximum capacity of 4 participants per week with a total of 45 participants enrolled in the study (30 in Study 1 and 10 in Study 2).

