#### **4.5 Study Visits**

**Screening:** Patients who have been referred or have volunteered for the study will be screened in person or by phone to verify that inclusion and exclusion criteria have been met.

**Consent procedures:** Each patient will be given a full verbal explanation of the study procedures, including risks, benefits, and alternatives, and will be given a copy of the approved written consent form. The patients will be given the opportunity to review the consent form and to discuss any questions or concerns with their own psychiatrist, our study investigators, or others if necessary prior to beginning study treatment procedures.

**Baseline:** Prior to the first treatment, depression severity will be assessed via a psychiatric interview, including completion of the HRSD-24 and MoCA, which will also verify inclusion and exclusion criteria. Immediately before treatment 1, the participant will complete the QIDS and a blood sample will be obtained from the IV line.

**Randomization (Study 1 only):** Participants who meet study criteria will be randomly assigned in blocks of 4 to either high or low dose isoflurane (High ISO/BS+ vs. Low ISO/BS-). We anticipate up to 15 participants in each arm; this sample size was defined by our prior study in which 8 participants were adequate to show significant antidepressant effects.

**Leukocyte Gene Expression:** Although our study is designed with EEG burst suppression as our primary target mechanism, we acknowledge that its effects must be mediated via specific neural pathways. Thus, we will explore possible neural and immune pathways associated with the antidepressant effects of deep anesthesia. Changes in full transcriptome leukocyte gene expression from pre- to post-treatment will be assessed from blood samples drawn before the first treatment and within 48 hours of the final (10th) treatment. In particular, we will examine the possible role of GABA-ergic and ATP-responsive ion channel pathways as well as other putative depression- or suicidality-linked neuroimmune pathways. We will also evaluate other ATP-responsive ion channels (purinergic, acid sensing and transient vanilloid receptor) or other

genes including IL-10 and other cytokines, SAT1, PTEN, MARCKS and MAP3K3 previously associated with refractory depression or suicidality by our group and others. [42918](#)

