High ISO/BS+ (n=15): The High ISO/BS+ group will receive isoflurane at the same level used in our previous study, with the initial vaporizer setting at 4%. End-tidal isoflurane concentration will be measured continually and is the best measure of alveolar concentration. Alveolar concentration will approximate effect site concentration. In this study we are directly measuring isoflurane effect on CNS electrical activity via the EEG (BIS) and burst suppression ratio is continually calculated and displayed. As the end tidal isoflurane concentration increases and the burst-suppression ratio increases, the vaporizer setting will be decreased. The goal is a burst-suppression ratio of 80%. Some burst suppression is seen at concentrations as low as 1MAC of isoflurane (1.15%) and most patients will achieve 80% BSR at 2 MAC or less (2.3%). These doses are well within the normal range for isoflurane use and are achieved on a daily basis in the O.R.s at this institution. As in the prior study by [name] et al , this condition of isoflurane-induced electrical quiescence will be maintained for 15 minutes.

Low ISO/BS- (n=15): ISO concentration will be titrated to maintain unconsciousness with burst suppression of  $\leq 20\%$ . This condition will be maintained for 15 minutes.

**5.1.2 Study 2. Open-Label Propofol Treatment:** Participants in the propofol treatment group will receive an induction dose of 2-3 mg/kg IV bolus, followed by propofol infusion at 100-400 mcg/kg/min. Additional boluses (0.5-2 mg/kg), administered every 2-3 minutes, may be necessary to achieve and maintain 80% burst suppression on EEG. At the end of the treatment, propofol administration will be discontinued and the participant will be allowed to awaken. Similar means of propofol induced burst-suppression is commonly and safely administered during neurosurgical procedures. Monitoring and supportive treatment will be consistent with clinical standards outlined by the American Society of Anesthesiologists as discussed above for participants in the main study. We will enroll up to 10 participants in the propofol pilot study.

**5.1.3 Anesthetic Emergence (All Treatments):** Emergence from isoflurane anesthesia into consciousness will be facilitated by the Aneclear device (QED 100™) according to FDA approved guidelines and as routinely used in the University of Utah operating rooms.

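### The interim safety look is labelled a midpoint but falls at 5 of 15 per isoflurane arm, and its undefined significance-based stopping rule would, on usual readings, miss most large excesses of harm

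*Combined protocol and SAP*

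**What the plan says.** Section 6.3 (Safety and Efficacy Monitoring) schedules one interim analysis "at the midpoint of this pilot investigation, after data is obtained from 5 participants in each of the treatment conditions". The rule attached to it is: "The study will be terminated if significantly greater negative outcomes are associated with either isoflurane treatment or propofol treatment". No negative outcome, comparator, test, significance level or sidedness is given for this rule, in 6.3 or in Section 7.

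The planned sizes are elsewhere. Section 2.1 has 15 per isoflurane arm, 30 in all. Section 4.5 gives the basis for that size: "We anticipate up to 15 participants in each arm; this sample size was defined by our prior study in which 8 participants were adequate". Section 5.1.2 says "We will enroll up to 10 participants in the propofol pilot study". Section 4.3 gives a total of 45, although its own components (30 and 10) add to 40. It also lets participants choose which study to join; only the isoflurane dose is randomised.

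Other safeguards are stated:
- Section 6: a review after the first 2 participants complete treatment, then every 6 months.
- Section 6.3: serious events reported to the DSMB and IRB within 5 days; moderate events, including worsening depression, reported to the DSMB; notice of individual deterioration within 10 business days; and withdrawal after a serious reaction to anesthesia.

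**The concern.** Two things do not fit together. The label says half-way, while the count is one third of the randomised comparison. And the only group-level stopping rule depends on a finding of significance at a sample size where an exact test has almost no room to reach it.

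The stake is false reassurance. A monitoring group could see harm in 3 of 5 participants on one isoflurane dose and none of 5 on the other, find p = 0.17, and record that the stopping rule was not met. The rule also sets isoflurane against propofol in its wording, so a literal reader might never compare the two randomised doses.

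**Working it through.** **Timing.** Inputs: 15 per isoflurane arm (2.1, 4.5), 10 on propofol (5.1.2), look at 5 per condition (6.3).

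- Each isoflurane arm: 5/15 = 33%; half would be 7.5.
- Study 1: 10/30 = 33%.
- Propofol: 5/10 = 50%.
- Both studies: 15/40 = 37.5%, or 15/45 = 33% on the stated total.

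The midpoint label is therefore reproduced for propofol only. It is reproduced overall if 5 is a minimum and enrolment runs at 30:10 = 3:1. When propofol reaches 5, isoflurane is then at 15, and (5 + 15)/40 = 50%, with 15/2 = 7.5 per isoflurane arm.

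**What triggers the rule.** The documents give no test, so I assume Fisher's exact test, two-sided 0.05, on a yes/no negative outcome. Of the 36 possible 5 v 5 tables, these matter in the harmful direction:

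| Events | Two-sided p | One-sided p |
|---|---|---|
| 3 v 0 | 0.167 | 0.083 |
| 4 v 0 | 0.048 | 0.024 |
| 4 v 1 | 0.206 | 0.103 |
| 5 v 0 | 0.008 | 0.004 |
| 5 v 1 | 0.048 | 0.024 |
| 5 v 2 | 0.167 | 0.083 |

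Only 4-0, 5-0 and 5-1 trigger. One-sided 0.05 gives the same three tables.

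**Chance of triggering.** With X events of 5 in the worse arm and Y of 5 in the other:

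P = P(X=4)·P(Y=0) + P(X=5)·[P(Y=0) + P(Y=1)]

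The harm rates are assumptions.

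- 50% v 10%: 0.15625 × 0.59049 + 0.03125 × 0.91854 = 0.121
- 60% v 10%: 0.2592 × 0.59049 + 0.07776 × 0.91854 = 0.224
- 60% v 20%: 0.2592 × 0.32768 + 0.07776 × 0.73728 = 0.142

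The same enumeration at other sizes, and with a one-sided p<0.10 trigger for comparison:

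| Harm | 5 v 5, two-sided 0.05 | 7 v 7, two-sided 0.05 | 8 v 8, two-sided 0.05 | 5 v 5, one-sided 0.10 | 8 v 8, one-sided 0.10 |
|---|---|---|---|---|---|
| 50% v 10% | 12% | 13% | 22% | 31% | 44% |
| 60% v 10% | 22% | 26% | 39% | 43% | 63% |
| 60% v 20% | 14% | 15% | 24% | 27% | 45% |

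Over a wider range at 5 v 5, two-sided 0.05: 30% v 10% gives 1.9%, 40% v 10% gives 5.5%, 80% v 20% gives 38% and 90% v 10% gives 74%.

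**Other readings of the rule.**
- Barnard's test also fails at 3-0 (p = 0.0625).
- An uncorrected chi-square, unreliable at these counts, adds 3-0 and 5-2 and so gives 31%, 43% and 27%.
- Propofol (5) against both isoflurane arms pooled (10), with the excess on propofol, gives 26%, 39% and 21% by two-sided Fisher, but that comparison is not randomised.
- For a continuous score at 5 v 5, 80% power needs a difference of about 2.0 SD; power at 0.8 SD is 20%.

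**False triggers.** With equal true harm of 10% to 40% in both arms, one-sided p<0.10 triggers 0.5% to 3% of the time per direction at 5 v 5, and 1.2% to 3.8% at 7 v 7.

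**The case against.** The midpoint wording can be defended. The two studies run concurrently at a planned 3:1, and 5 per condition can be read as the point at which the slowest condition gets there. Nothing in 6.3 says that isoflurane data beyond 5 per arm would be set aside. This stands as a possible reading, so a reader who infers a plain arithmetic error goes further than the text allows. But self-selection between studies means that nothing secures the 3:1 ratio, and the text does not state this reading. Even granting it, 7 or 8 per arm leaves the two-sided test triggering at 13% to 39% in the three main scenarios.

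The low sensitivity rests on a test, a level and harm rates that the documents do not supply. That also stands. The word *significantly* may mean a judgement by the monitoring group. Section 9.1 gives frequencies only for anesthetic effects (1-10% for common ones, below 1/10,000 for the gravest), and none for worsening depression. The percentages show what the usual reading would deliver; they are not properties of a rule the protocol has defined.

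The strongest objection concerns reach. A reader might infer that harm would go unnoticed or that participants lack protection. The documents do not support that: the event reporting, reviews, deterioration notices and withdrawal in Sections 6 and 6.3 do not depend on this rule. None of them, however, is a group-level boundary.

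**Conclusion.** The point holds for the group-level rule and should be corrected; it does not show that safety monitoring as a whole is deficient. The look is at one third of Study 1 and half of Study 2 unless an unstated minimum and an unsecured enrolment ratio are assumed. The rule is undefined in outcome, comparator, test and boundary. Read as a two-sided Fisher test at 0.05, it would miss assumed excesses of 50% v 10%, 60% v 10% and 60% v 20% about 88%, 78% and 86% of the time at 5 v 5.

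It would be too strong to say that the rule cannot trigger, since it does so about 74% of the time at 90% v 10%. Nor would moving the look to a true midpoint cure it. The timing arithmetic is firm; the percentages are conditional on the assumed test and rates.

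**What to change.** In Section 6.3:

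1. State the look as one third of Study 1 and half of Study 2, or state that it uses all isoflurane data available when the last condition reaches 5.
2. Define the negative outcome. Replace the significance test with a predefined High versus Low trigger that leads to review by the monitoring group, and tabulate its operating characteristics. One-sided exact p<0.10 is an example, with the gains shown above; it still misses 57% to 73% of the three main scenarios at 5 v 5. The sponsor and monitoring group choose the boundary.
3. For propofol, which has no randomised comparator, review the observed count with an exact confidence interval. Even 0 of 5 has an upper 95% limit of 1 − 0.025^(1/5) = 52%.
4. Before deterioration is counted as a negative outcome, reconcile 6.3, which defines it by QIDS or HRSD-24 scores falling under baseline, with 2.1 and 7.1, which treat a reduction in score as response. As worded, improvement could be counted as harm.

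The cost is a few sentences and one small table. With the example trigger, an unnecessary review has a probability of about 0.5-3% per direction at 5 v 5 and 1-4% at 7 v 7 when both arms have 10-40% harm, and twice that if an excess in either arm is watched.

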## **4. General Study Design**

To determine if the antidepressant effects of deep anesthesia are related to burst suppression (BS+) we will conduct two concurrent studies: 1) prospective, randomized, double-blind study will evaluate the role of burst suppression using isoflurane treatments at 2 doses (high dose ISO/BS+ vs low dose ISO/BS-) on symptoms in participants with moderate to severe depression, and 2) an open-label pilot study examining the anti-depressive effects of propofol anesthesia, BS+ same as high dose ISO/BS+ on symptoms in participants with moderate to severe depression.

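### The only interim analysis tied to a stopping statement waits for 5 propofol participants, so Study 1's look can come late or not at all for a reason outside Study 1

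*Combined protocol and SAP*

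**What the plan says.** Section 6.3 of the combined protocol and SAP states that "An interim data analysis will be performed at the midpoint of this pilot investigation", and defines that moment as "after data is obtained from 5 participants in each of the treatment conditions". The next sentence is the only study-level termination statement: "The study will be terminated if significantly greater negative outcomes are associated with either isoflurane treatment or propofol treatment". Because it names propofol as well as isoflurane, the natural reading is three conditions: High ISO/BS+, Low ISO/BS- and propofol.

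Section 4 says "we will conduct two concurrent studies". On entry, section 4.3 says "Participants will be informed that there are two study options and that they will be able to decide which one they will participate in", and gives no quota or ratio. Section 5.1.2 says "We will enroll up to 10 participants in the propofol pilot study", which is a ceiling and not a target. No section pauses Study 1 enrolment until the look, gives Study 1 its own trigger, or says what happens if propofol does not reach 5.

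Other oversight is planned. Section 6 has study data monitored after the first 2 participants finish treatment and 6-monthly after that. Section 6.3 adds serious adverse event reports within 5 days, reporting of moderate events, notice of clinical deterioration within 10 business days, and 6-monthly progress reports.

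**The concern.** Randomisation in blocks of 4 keeps the two isoflurane arms in step, so Study 1 alone would reach 5 per arm at a predictable point. The propofol count is set by patient preference and is outside the control of Study 1. Requiring all three counts ties the randomised trial's look to the slowest-filling group, which may be the one in the other study.

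At stake is how much of Study 1 remains to be influenced when the one analysis with a termination statement is done. If most or all of the 30 are already enrolled, a finding of harm can change little for Study 1. The concern is the trigger only. It does not concern the test used at the look.

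**Working it through.** **The plan's own timing.** Section 6.3 equates the midpoint with 5 per condition. Against the planned sizes (15 per isoflurane arm, 10 propofol, 40 in all), that is 5/15 = 33% of each isoflurane arm, 5/10 = 50% of propofol and 15/40 = 37.5% overall. Section 4.3 also gives a total of 45, although its parts sum to 40; 15/45 = 33%. Only propofol is at its midpoint.

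**Inputs from the documents.** Study 1 cap 30; blocks of 4; course of 3 weeks; entry of 1 to 4 per week across both studies (section 4.3).

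**Assumptions.** A share p of entrants chooses propofol (10% to 50% shown; 25% matches 10 of 40). Entry is evenly spaced, there is no dropout, and data count once the 3-week course is complete.

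**Step 1: Study 1 alone.** Two full blocks give 4 per arm at participant 8. In the third block the first two allocations differ with probability 2/3, giving 5 per arm at participant 10. Otherwise it takes 11. So m = 10 or 11, with mean 10 × 2/3 + 11 × 1/3 = 10.33.

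**Step 2: waiting for propofol, before any lag.** Let K be the number of isoflurane entries before the 5th propofol entry. P(K ≥ k) = P(at most 4 propofol among the first k + 4 entries). For k = 30 this is 75% at p = 10%, 41% at 15%, 16% at 20%, 4.9% at 25% and 0.4% at one third. If recruitment ends when Study 1 is full, these are also the chances that the look never happens.

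**Step 3: add the course.** While the last needed participant is treated, L = 3 × 1 = 3 or 3 × 4 = 12 people enter across both studies, of whom B ~ Binomial(L, 1 - p) are isoflurane. Study 1 enrolment at the look is N = min(30, max(K, m) + B). Each cell below gives 1 per week, then 4 per week.

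| Propofol share | Mean N of 30 | P(N ≥ 24) | P(N = 30) |
|---|---|---|---|
| 10% | 28.5, 29.6 | 90%, 98% | 80%, 92% |
| 15% | 25.3, 28.4 | 67%, 88% | 48%, 72% |
| 20% | 21.3, 26.3 | 40%, 70% | 21%, 45% |
| 25% | 17.9, 23.8 | 19%, 47% | 7%, 22% |
| 33% | 14.3, 20.2 | 4%, 16% | 1%, 4% |
| 50% | 12.0, 16.5 | 0%, 0.3% | 0%, 0% |

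The formula ignores the propofol ceiling of 10. Simulation with that ceiling, sending later entrants to Study 1, raises the means to about 14-21 at 33% and 13-21 at 50%. The last column is unchanged to the nearest percentage point or so.

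**Step 4: a Study 1-only trigger.** Mean enrolment is 10.33 + L(1 - p). At 1 per week this runs from 10.33 + 3 × 0.5 = 11.8 to 10.33 + 3 × 0.9 = 13.0. At 4 per week it runs from 10.33 + 12 × 0.5 = 16.3 to 10.33 + 12 × 0.9 = 21.1 (about 19-21 if later entrants go to Study 1 once propofol is full). The maximum is 11 + 12 = 23, whatever participants choose.

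**Step 5: can the other reviews stand in?** At 1 per week the first 2 completers are seen at about week 2 + 3 = 5. The next 6-monthly review is at about week 5 + 26 = 31, with about 31 of 40 enrolled. At 4 per week all 40 are enrolled by week 40/4 = 10, before any 6-monthly review.

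**The case against.** A reader might infer that this is the trial's only safety review, so that a late look leaves participants unprotected. The documents do not support that. The reviews and notices in sections 6 and 6.3 run whatever the propofol count, and individual symptom monitoring continues throughout. What remains is narrower: none of them carries a stated criterion for stopping the study, two completers cannot support an arm comparison, and the 6-monthly reviews can themselves be late.

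A reader might also infer that Study 1 will be nearly complete by the time of the look. That depends on a share the documents do not give. At the planned 25%, full enrolment is a minority outcome; at one third or more it is unlikely. Section 4.3 gives reasons both ways. Only high-dose isoflurane is described as having preliminary evidence, but choosing that study carries a 50:50 chance of the low dose, while propofol is open-label at a burst-suppression dose. This objection stands as to size. It does not remove the dependence on choice.

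It can be said that the word midpoint shows no drift was intended. It does, but the count in the same sentence is the operative condition, and the two agree only for propofol.

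Finally, a reader might want each look's decision confined to its own study. The current statement ends the study if either agent shows harm, and propofol and High ISO/BS+ share the 80% burst-suppression target, so a wider reach may be intended. Nothing here justifies narrowing it.

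**Conclusion.** The point holds as a defect in the trigger. The one analysis with a termination statement depends on a count that is driven by choice, has no minimum and belongs to a different study, so Study 1's look can be late or absent.

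At the planned 25% share, waiting for propofol moves the look later by about 5 Study 1 participants on average (17.9 - 12.6 = 5.3 at 1 per week; 23.8 - 19.3 = 4.5 at 4 per week). It also creates a 7-22% chance of full enrolment that would otherwise be nil. Late timing becomes the likely result at about 15% or below and is unlikely at one third or above. These figures rest on the assumed share, even entry, no dropout and data being counted at the end of the 3-week course. The dependence itself needs none of those assumptions. It is worth correcting before enrolment, but the continuing event reporting keeps it from being critical.

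**What to change.** In section 6.3, replace the single trigger with two:

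- The Study 1 look takes place when 5 High ISO/BS+ and 5 Low ISO/BS- participants have post-treatment data, whatever the propofol count.
- A separate propofol look takes place when 5 propofol participants have post-treatment data.

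Reconcile the word midpoint with these counts, since 5 per arm is one third of Study 1. Leave the scope of the termination statement unchanged.

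The cost is one sentence and possibly one extra short monitoring report. No participants, visits or procedures are added.
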